The purpose of the prescreening telephone call will be to further explain the study to the parents, confirm their interest in taking part, and determine their child's eligibility. We will introduce ourselves as research scientists from Rainbow Babies and Children's Hospital, University Hospitals Cleveland Medical Center and Case Western Reserve University conducting a research study comparing the brains of children born at full term, with brains of children born prematurely. We will tell them we are looking at how certain parts of the brain look and how they work. We will tell the interested individual that we plan to take pictures of the brain using an MRI scanner. We will also record EEG, which measures brain waves, by having the child wear a stretchy cap on their head with gel placed into little holes in the cap. These same tests are often done in medical practice. During the MRI scan, we will ask the child to do a memory test. We will also ask children to play a timed board game during the EEG recording. While the child is being tested, we will ask parents to fill out questionnaires about the child's health, behavior, and sleep.

We will describe that an MRI involves using a strong magnet and radio waves to produce a picture of body parts. EEG involves recording electrical activity of the brain from the scalp. This research project will involve taking pictures of a person’s head combined with patterns of brain activity recorded on the surface of their head. This will help us gain a better understanding of the human brain. We will tell the parents/children that we expect to enroll at least 20 children for this study who were born prematurely and 10 children who were born at or near their due date. We will emphasize that participation in this study is voluntary.

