2. *Describe the methods that will be used to identify potential research participants.*

The proposed study will involve participation of male and female children to achieve a total number of 30 complete data sets. All children to be studied will range in age between 9-17 years during the funding period. Study participants will include survivors of preterm birth, with birth gestations of 22-30 weeks and birth weights appropriate for gestational age.

We intend to focus our recruitment on 20 children who were born preterm with birth gestational ages between 22-30 weeks, are survivors from Rainbow Babies & Children's Neonatal Intensive Care Unit, and have been followed since birth. The children invited for participation will be part of the maintained cohort for whom continuous oxygen saturation data were collected in their first 8 weeks of postnatal life. Co-Investigator [name] maintains this research cohort. In the event that we cannot enroll 20 children who have continuous oxygen saturation data from their neonatal hospital stay, [name] will assist us to identify other preterm survivors who are similar to the study group population but may be between 9 and 17 years old and/or have birth gestations up to 30 weeks. We will also recruit for other preterm survivors via study flyers and advertisements.

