diffusion tensor imaging with subtraction analyses and fMRI coupled with high-density electroencephalographic (EEG). We hypothesize that dopaminergic projections, originating in the substantia nigra pars compacta (SNpc) and ventral tegmental area (VTA), projecting primarily to the striatum and prefrontal cortex (PFC) to modulate motor control and cognitive function, will be structurally and functionally impaired. The primary sample for our proposed study is derived from a cohort of preterm infants admitted to Rainbow Babies & Children’s Hospital between 2004 and 2009 at a gestational age of 23 to 28 weeks. The purpose for developing the original cohort was to establish the effects of maintaining oxygen saturation levels between 85%-95% to decrease the development of retinopathy of prematurity. Oxygen saturation levels and desaturation events were recorded continuously from the first day of life to 8 weeks’ postnatal age. If recruitment targets for study group children cannot be achieved, we will engage the assistance of Co-Investigator [name] to recruit additional former preterm children currently 9 to 17 years old with birth gestational age between 23-30 weeks and birth weight appropriate for gestational age (AGA for comparison, we plan to recruit healthy control children within the age range of the eligible former preterm children. Our findings will provide new insight into the neural basis of cognitive dysfunction reported in many former preterm children who experienced mild to moderate hypoxic insults.

APPROACH: Eligible and interested former preterm children will be identified by [name] and [name]. These children are prematurely born survivors from Rainbow Babies & Children's Neonatal Intensive Care Unit, and have been followed since birth. Children in this cohort have already participated in research, and remain willing to participate in future projects. [name] and/or [name] will provide our research team with names/contact information of interested individuals. We will contact those individuals by telephone to describe the study and conduct a prescreening.

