- Health plan beneficiary number
- Account number
- Certificate/license number
- Any vehicle or other device serial
- Device identifiers or serial numbers
- Web URL
- Internet protocol (IP) address
- Finger or voice prints
- Photographic images
- Other: Any characteristic that would uniquely identify the individual

2. *List all other data to be collected for the research study (e.g. laboratory values, physician notes, length of stay, etc.).*

- Magnetic Resonance Imaging, specifically T1 structural scan, Diffusion Tensor Imaging (DTI), and functional Magnetic Resonance Imaging-Blood Oxygen Level Dependent (fMRI-BOLD)
- High density electroencephalography (HD-EEG)

- Neurobehavioral Assessments of child: Verbal n-back; Grooved Pegboard task
Parent report of child behavior (parent-report): Child Behavior Checklist, Vanderbilt Assessment Test, Child’s Sleep Habits Questionnaire (for children ages 9-12), Pediatric Sleep Questionnaire (for children ages 9-17).
- Urine collection (to determine pregnancy exclusion for female child participants)

Data Analysis Plan

1. Describe the data analysis plan, including any statistical procedures. Provide a power analysis if applicable.
2. If applicable, describe the primary and secondary study endpoints including safety endpoints.

Our intent in this exploratory cross-sectional two-arm pilot study is to develop sufficient Scientific Rigor to support a future study appropriately powered to account for our proposed primary outcome measures and co-variates. Our sample will include 20 prematurely born children who experienced hypoxic insults during postnatal life. To allow comparison to “normative” expectations, we will compare these 20 former preterm children with 10 healthy term-born controls without exposure to hypoxia and of similar age, sex, race distribution as the preterm group. Data from these 30 children will be used to develop appropriate sample sizes, using actual rather than predictive data, for future studies characterizing neural structure and function following postnatal hypoxic insults.

Specific structural and functional characteristics used in our analyses will include

- apparent diffusion coefficients and fractional anisotropy generated from DTI data
- fMRI-BOLD, measured during the pediatric verbal n-back, and HD-EEG sLORETA

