- neurobehavioral assessment results (grooved pegboard test, verbal n-back, Child Behavior Checklist, Vanderbilt Assessment test, Child’s Sleep Habits Questionnaire, Pediatric Sleep Questionnaire)

Covariates include 1) age, 2) sex, 3) race, 4) preterm vs. term birth, and 5) frequency of hypoxic insults (< 5000 versus ≥ 5000) during the first 8 weeks of life within the preterm group. The continuous outcome measure variables will be summarized using descriptive statistics (mean, standard deviation, median, interquartile range). Frequency analyses and stem-n-leaf graphs will characterize data distributions. Skewed continuous variables will be transformed to satisfy normality assumptions of hypothesis testing. Outcome measures for the two groups will be compared graphically using box plots. We will perform hypothesis tests for equality of data distribution for the two groups using t-tests or Wilcoxon sign rank test, as appropriate, with a significance level of 10%.

As we are interested in the differences of above mentioned outcome measures in two groups, we will focus on effect size estimation for the differences of our measures. To detect significant effect size, we will perform regression analysis on the outcomes of interest with the primary covariate of interest being group membership (preterm vs. term birth). In the regression analyses, we will control only for significant confounding effects of age, sex, race, and frequency of hypoxic insults. Using regression analyses, we will determine point

estimates, regression coefficients (beta), as well as 90% confidence interval of betas. The confidence intervals will be main estimated effect size or the differences in outcomes in two groups due to preterm and term birth.

Confidentiality of Specimens and Banking

I am not storing specimens in this research project – *please leave the rest of this section blank*

Describe:

- The source of the specimens*
- Where the specimens will be stored*
- How long the specimens will be stored*
- How the specimens will be labeled*
- How the specimens will be accessed*
- Who will have access to the specimens*
- When and how will the specimens be destroyed*
- How will the specimens be transported (Please note if transporting specimens, a Material Transfer Agreement (MTA) is required).*

Describe:

- The procedures to release specimens including:*
 - i. The process to request a release*
 - ii. Approvals required for a release*
 - iii. Who can obtain specimens*

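### Hypoxic burden is analysed only as below versus at or above 5000 events, with no reason for the cut and no continuous analysis; the information lost within the preterm group could be substantial but depends on features the protocol does not give

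*Combined protocol and SAP*

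**What the plan says.** Under Data Analysis Plan, the last of the five listed covariates, defined for the preterm children only, is "frequency of hypoxic insults (< 5000 versus ≥ 5000) during the first 8 weeks of life". The regression's main term is group membership (preterm versus term). Hypoxia frequency, like age, sex and race, is adjusted for only where its confounding effect is significant. The same section says that skewed continuous variables will be transformed, that 90% confidence intervals will be reported, and that the study is an exploratory pilot meant to inform later sample sizes. It gives no reason for 5000 and no analysis of the count on a finer scale.

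A finer measure exists. Study Design, Procedures and Timeline says of the original cohort: "Oxygen saturation levels and desaturation events were recorded continuously from the first day of life to 8 weeks".

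On numbers, the analysis plan states: "Our sample will include 20 prematurely born children who experienced hypoxic insults during postnatal life". Recruitment Methods reports 42 cohort children available, but also has a fallback that begins: "In the event that we cannot enroll 20 children who have continuous oxygen saturation data from their neonatal hospital stay". Recruits added that way need not have a count, so the number with one may be below 20.

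**The concern.** Postnatal hypoxia is the exposure the study is about. The design section asks whether differences in birth events and newborn oxygen levels lead to impairment. The preterm-term contrast cannot separate oxygen levels from prematurity itself; variation in hypoxia among the preterm children is the only information here that bears on that. A two-class variable treats a child just over the cut and one far above it as equally exposed.

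Three things are at stake: the precision of the exposure-outcome estimate in a group of about 20 or fewer; the value of the pilot for planning, since two classes give no slope per unit of exposure; and the significance rule for covariates, because a weaker version of the variable is more likely to be dropped from the model.

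**Working it through.** The protocol states no power, effect size or information figure for the hypoxia count, so there is no figure to reproduce.

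**Inputs from the protocol:** cut at 5000 events; 20 preterm children planned; significance level 10%.

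**Assumptions, none given in the protocol:** shape of the count distribution; share p of children at or above 5000; correlation rho between count and outcome; a two-sided test (consistent with the 90% intervals).

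**Step 1. Information kept by the split.** For a weak linear effect this is the squared correlation between the count and the indicator of being at or above the cut. For a normal count, or a log-normal count analysed on the log scale, it equals φ(z)² / [p(1 − p)], where z is the cut on the standard normal scale and φ is the normal density.

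| Share above the cut | φ(z) | Calculation | Kept | Effective n out of 20 |
|---|---|---|---|---|
| 50% | 0.399 | 0.1592 / 0.25 | 64% | 12.7 |
| 30% | 0.348 | 0.1209 / 0.21 | 58% | 11.5 |
| 20% | 0.280 | 0.0784 / 0.16 | 49% | 9.8 |
| 10% | 0.175 | 0.0308 / 0.09 | 34% | 6.8 |

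**Step 2. Power for the within-preterm slope.** Bivariate normal simulation, t-test of the slope, two-sided 10%, 20,000 data sets; results are good to about one percentage point.

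| n | rho | Continuous | Median cut | 70/30 cut |
|---|---|---|---|---|
| 20 | 0.3 | 37% | 27% | 25% |
| 20 | 0.4 | 57% | 41% | 37% |
| 20 | 0.5 | 76% | 57% | 52% |
| 20 | 0.6 | 90% | 73% | 69% |
| 10 | 0.5 | 46% | 33% | 30% |

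The row with n = 10 illustrates the case where many recruits have no count. At n = 20 and rho = 0.5, an 80/20 cut gives about 46% and a 90/10 cut about 33%.

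**Step 3. Other shapes, linear effect on the raw count.**
- Right-skewed counts (gamma, exponential, log-normal): the loss is 35% to 46% at the best cut and 41% to 73% at the median.
- Uniform count cut at the median: 25%.
- Two clusters centred 1.5 or 2 SD either side of the midpoint, cut there: 25% and 19%.

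**Step 4. A true step at the cut.** With a 1 SD step at the median and n = 20, the split has power 67% and the linear term 49%. Here the split loses nothing and does better.

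**The case against.** Hypotheses 1 and 2 and both aims compare preterm with term children; no dose-response hypothesis is stated. Hypoxia frequency is one covariate among several in an exploratory pilot that emphasises estimation, so the power figures describe an analysis the plan does not specify. The cut is at least prespecified. A continuous term also assumes a shape, and with 20 or fewer children a few extreme counts can dominate it. All of this stands: it limits the consequence and is a reason to keep the split in a secondary role. It does not explain why 5000 was chosen or why the finer measure goes unused. Skew is no reason either, since the plan already provides for transformation.

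A reader might infer more than the protocol supports:

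- **That the cut discards a third or more of the information as a matter of fact.** That needs the distribution and the dose-response shape, and neither is given. Steps 3 and 4 show plausible cases below a third, and one with no loss.
- **That the two-class variable leaves residual confounding in the preterm-term contrast.** The covariate is defined only within the preterm group, and postnatal hypoxia follows preterm birth as the proposed mechanism. It is not a common cause of group and outcome. A finer version changes what the group coefficient means; it does not remove confounding from it.
- **That the sample with counts could exceed 20.** The prescreening text says "we expect to enroll at least 20 children for this study who were born prematurely", but that is enrolment wording and does not promise more children with oximetry.

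**Conclusion.** The point holds in a limited form. A continuously recorded exposure, central to the study's question, is used only in two classes, at an unexplained cut and with no alternative analysis.

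For a roughly normal or log-normal count with a linear effect, the loss is about 36% of the exposure information at a median cut, 42% at 70/30 and 66% at 90/10. At n = 20 and a median cut, that costs roughly 10 to 19 percentage points of power for correlations of 0.3 to 0.6. The loss falls to 19% to 25% for a flat or two-cluster count cut near the middle, and to nil for a true step at 5000. The protocol does not say which case applies.

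The harm is confined to the exposure-outcome estimate among preterm children and to the chance that hypoxia survives the significance rule. The unadjusted preterm-term comparison loses nothing. The change is worth making because it is cheap and bears on the exposure of interest; the study's main contrast does not depend on it.

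**What to change.** In the Data Analysis Plan, add a model restricted to preterm children with oximetry in which the event count is continuous (log-transformed if skewed), and report its coefficient with a 90% confidence interval. State how many children contribute a count. Keep the split at 5000 as a secondary analysis, give the reason for that value, and report how many children fall on each side.

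The cost is a change of wording. Placing a child above or below 5000 already requires a count, so no new data collection is needed. The downside is that a continuous term assumes a shape and can be sensitive to extreme counts at this sample size. The log scale reduces that sensitivity, and the retained split covers the possibility of a threshold.

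### The only named hypothesis test is unadjusted while the main 90% confidence interval is adjusted, and the plan does not say which settles significance

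*Combined protocol and SAP*

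**What the plan says.** All of this is in the Data Analysis Plan of the combined protocol and SAP.

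- **Design.** The comparison is 2:1 and not randomised: "we will compare these 20 former preterm children with 10 healthy term-born controls".
- **First analysis.** After the descriptive summaries and box plots comes "We will perform hypothesis tests for equality of data distribution for the two groups using t-tests or Wilcoxon sign rank test, as appropriate". The level set for these tests is 10%. No covariates enter.
- **Second analysis.** The next paragraph says "we will focus on effect size estimation for the differences of our measures", and then "To detect significant effect size, we will perform regression analysis on the outcomes of interest with the primary covariate of interest being group membership".
- **Adjustment.** In that regression "we will control only for significant confounding effects of age, sex, race, and frequency of hypoxic insults". The threshold for significant is not given. Hypoxia frequency (below 5000 versus 5000 or more) is defined only within the preterm group.
- **Output.** The regression delivers "estimates, regression coefficients (beta), as well as 90% confidence interval of betas", and "The confidence intervals will be main estimated effect size or the differences in outcomes in two groups due to preterm and term birth".

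The plan does not say which analysis supports or refutes Hypotheses 1 and 2 in the Purpose section, or what to do when the two disagree. Hypothesis 1 is itself worded in terms of a significant reduction.

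**The concern.** A 90% confidence interval for the group coefficient is also a two-sided 10% test, and the plan introduces the regression in the language of significance. Each outcome therefore gets two significance readings of the preterm-term difference, one crude and one adjusted. The words hypothesis test and significance level belong to the crude reading, while the word main belongs to the adjusted one.

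A report that follows the plan could print p < 0.10 beside a main interval that includes zero, or the reverse, with no rule for the reader. The crude test is also the weaker basis for a decision here. Controls respond to flyers and are only approximately matched on age over a 9 to 17 year range, so an age difference between the groups goes straight into the crude p-value. The choice matters beyond this study, because these data are meant to set the sample size of a later one.

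**Working it through.** **Inputs from the plan.** 20 preterm and 10 term children; 10% level for the crude test; 90% interval for the regression; candidate covariates age, sex, race and hypoxia frequency.

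**Assumptions, since the plan gives no figures.** Two-sided tests; the share of outcome variance explained by covariates (R²); the size of any age imbalance; the selection threshold; the split of the preterm group on hypoxia. The plan names the signed-rank test, which is for paired data; the rank-sum test was used for these independent groups.

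**Step 1: the level.** 1 − 0.90 = 0.10, so the interval excludes zero exactly when the two-sided p-value of the group coefficient is below 0.10. Both readings are at 10%. The plan states no power calculation to reproduce.

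**Step 2: bounds if either result may be cited.** If the two readings always agreed, the rate would be 0.10. If they were independent it would be 1 − 0.90² = 0.19. The upper bound is 0.10 + 0.10 = 0.20. They use the same children, so the value in between must be simulated.

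**Step 3: simulation with no true difference.** 8,000 replicates per setting; age uniform on 9 to 17; all of R² due to age; pooled t-test against least squares with group, age, sex and race. The imbalance setting adds one year to the preterm group, capped at 17.

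| R² of age | Either, no age imbalance | Either, preterm about 1 year older | Crude alone, preterm about 1 year older |
|---|---|---|---|
| 0 | 0.125 | 0.134 | 0.106 |
| 0.2 | 0.142 | 0.175 | 0.134 |
| 0.4 | 0.162 | 0.226 | 0.173 |

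Under the age imbalance the adjusted regression alone stays at about 0.10. The Monte Carlo standard error near 0.15 is √(0.15 × 0.85 / 8000) = 0.004.

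**Step 4: cross-check.** A second simulation spread R² equally over age, sex and race, with no imbalance and fixed covariates. At R² = 0, 0.2 and 0.4 the either rate was 0.121, 0.147 and 0.156 with the t-test, and 0.122, 0.146 and 0.160 with the rank-sum test (4,000 replicates). The two readings disagreed in 0.050, 0.089 and 0.114 of null data sets with the t-test. The identity P(either) = ½[P(crude) + P(adjusted) + P(disagree)] confirms the first of these: ½(0.095 + 0.097 + 0.050) = 0.121.

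**Step 5: a true difference of 0.65 SD, in the setting of step 3.** The readings disagree in 17.6% of studies at R² = 0.2 and 26.3% at R² = 0.4. Power, crude then adjusted, is 0.497 and 0.536 at R² = 0.2, and 0.484 and 0.630 at R² = 0.4. At R² = 0 a repeat run gave 0.49 and 0.46, so adjustment costs a little when the covariates explain nothing.

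**Step 6: is naming the regression enough?** In the setting of step 4, with covariates kept only at p < 0.10 and half of the preterm group at 5000 or more events, the regression alone rejected in 0.130, 0.135 and 0.138 of null data sets at R² = 0, 0.2 and 0.4. Without the hypoxia covariate the figures were 0.114, 0.116 and 0.111. With fixed covariates and no hypoxia term they were 0.097, 0.103 and 0.100. Naming the regression while keeping the planned selection therefore does not restore 10%.

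**Step 7: meaning of the group coefficient.** Let G = 1 for preterm and H = 1 for preterm with 5000 or more events, and write the mean as a + bG + cH. Term children have mean a, preterm with fewer events a + b, and preterm with more events a + b + c. So b compares only the less exposed preterm children with term. The overall preterm-term difference is b + qc, where q is the share of preterm children at 5000 or more.

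**The case against.** The strongest reply is that the plan already has an order of precedence. It says the focus is effect-size estimation, makes group membership the primary covariate of the regression, and calls the regression intervals the main estimate. The t-test sentence closes a paragraph of descriptive statistics and plots. Crude results followed by adjusted results are ordinary reporting, and because they estimate different quantities, a disagreement is not in itself an error.

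Most of this stands. A reader might infer that nothing in the plan says which analysis matters; that goes too far, since precedence for estimation is stated. A reader might also infer that the false-positive rate for one outcome is above 10% as planned. The duplication alone does not produce that: it takes a rule that either result may be used to claim a difference, and the plan states no such rule.

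The largest rates in step 3 also need care. In the imbalance setting the either rate rises from 0.142 to 0.175 at R² = 0.2 (0.033 more) and from 0.162 to 0.226 at R² = 0.4 (0.064 more). That increase comes from confounding of the crude test, not from testing twice. The plan intends controls of similar age, sex and race, so a one-year gap is a possibility and not an expectation.

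What the reply does not answer is that the only named test and the only stated level sit on the crude comparison. Precedence for estimation does not tell the reader which result counts as significant.

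**Conclusion.** The point holds in a limited form. The same contrast is analysed twice at 10%; the regression leads for estimation but not for significance, and no rule covers disagreement. A crude p-value that contradicts the main adjusted interval can therefore arise when the plan is followed exactly.

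The error-rate consequence is conditional. If either result may be cited, the null rate for one outcome is about 12 to 16% instead of 10%, with no age imbalance, covariates fixed at age, sex and race, and age R² between 0 and 0.4. Separately, with preterm children about a year older and R² of 0.2 to 0.4, the crude test alone rejects in about 13 to 17% of null studies while the adjusted model stays near 10%. The R² values, the age gap and the 0.65 SD difference are assumptions, not figures from the plan.

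Severity is low: the study is an exploratory pilot without a confirmatory claim, and a few points on a 10% level will not mislead badly. The correction is nonetheless cheap and fits the plan's stated focus on estimation.

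**What to change.** In the Data Analysis Plan:

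1. State that, for each outcome, the group coefficient of the regression is the deciding contrast, and that its p-value (two-sided, 10%) and 90% interval come from the same model, so they cannot disagree.
2. Fix the covariates of that model in advance as age, sex and race, in place of keeping only significant ones.
3. Take hypoxia frequency out of the preterm-term model and examine it within the preterm group, among children who have the recordings, so that the group coefficient still means preterm versus term.
4. Label the unadjusted t-test and Wilcoxon results descriptive or supportive, reported beside the box plots and not used to call a difference significant.

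**Cost.** A few sentences, with no new data and no more children. With race coded as two categories, the residual degrees of freedom fall from 30 − 2 = 28 to 30 − 5 = 25. Power is slightly lower if the covariates explain nothing (0.46 against 0.49 at 0.65 SD). A difference that appears only in the crude test can no longer be called significant.
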